10.8 List of Abbreviations and Definition of Key Study Terms

List of Abbreviations

Abbreviations	Description of abbreviations
ADE	adverse device effect
ADL	activities of daily living
AE	adverse event
ALP	alkaline phosphatase
ALT	alanine aminotransferase
API	Astellas Pharma Inc.
AST	aspartate aminotransferase
AT	aminotransferases
BCRP	breast cancer resistance protein
CA	Competent Authorities
CBD	cannabidiol
CFR	Code of Federal Regulations
CI	confidence interval
CIOMS	Council for International Organizations of Medical Sciences
CL _R	renal clearance
CRO	contract research organization
CSR	clinical study report
CYP	cytochrome P450
DILI	drug-induced liver injury
ECG	electrocardiogram
eCRF	electronic case report form
EMA	European Medicines Agency
FAS	full analysis set
FDA	Food and Drug Administration
FSH	follicle-stimulating hormone
GCP	Good Clinical Practice
GI	gastrointestinal
GMP	Good Manufacturing Practices
HRT	hormone replacement therapy
IB	Investigator's Brochure
ICF	informed consent form
ICG	indocyanine green
ICH	International Council for Harmonisation of Technical Requirements for Pharmaceuticals for Human Use
IEC	Independent Ethics Committee
INR	international normalized ratio
IP	investigational product
IRB	Institutional Review Board
IRT	interactive response technology
ISN	international study number

Abbreviations	Description of abbreviations
LA-CRF	liver abnormality case report form
LN	lymph node
MATE	multidrug and toxin extrusion
NCI-CTCAE	National Cancer Institute - Common Terminology Criteria for Adverse Events
NIR-F	near-infrared fluorescence
OAT	organic anion transporter
OATP	organic anion transporting polypeptide
OCT2	organic cation transporter 2
P-gp	P-glycoprotein
QA	quality assurance
QC	quality control
QTL	quality tolerance limit
SAE	serious adverse event
SAF	safety analysis set
SAP	statistical analysis plan
SBR	signal background ratio
SLN	sentinel lymph node
SoC	Standard of Care
SOP	standard operating procedure
SPECT	single photon emission computed tomography
SUSAR	suspected unexpected serious adverse reaction
TBL	total bilirubin
Tc-99mSC	technetium-99m sulfur colloid
TEAE	treatment-emergent adverse event
TNM	tumor, nodes and metastases
UADE	unanticipated adverse device effect
ULN	upper limit of normal
USM	urgent safety measure
VRC	Visualization Review Committee
WOCBP	women of childbearing potential

Definition of Key Study Terms

Terms	Definition of Terms
Baseline Assessment	Assessments of participants as they enter a study before they receive any treatment.
Endpoint	Variable that pertains to the efficacy or safety evaluations of a study. Note: Not all endpoints are themselves assessments since certain endpoints might apply to populations or emerge from analysis of results. That is, endpoints might be facts about assessments (e.g., prolongation of survival).
Enroll	To register or enter a participant into a study.
Screen failure	Potential participant who signed the ICF, but did not meet 1 or more criteria required for participation in the study and was not enrolled.
Screening	A process of active consideration of potential participants for enrollment in a study.
Screening period	Period of time before entering the investigational period, usually from the time when a participant signs the consent form until just before the test product or comparative drug (without randomization) is given to a participant.
Study period	Period of time from the first study site initiation date to the last study site completing the study.
Variable	Any quantity that varies; any attribute, phenomenon or event that can have different qualitative or quantitative values.

	4.8.3	Analysis of Pharmacokinetics	19
	4.9	Interim Analysis	19
	4.10	Sample Size Determination · · · · · ·	19
	4.11	Additional Conventions	19
	4.11.1	Missing Data ··································	19
	4.11.2	2 Analysis Windows ····· ····	20
5	SUF	PPORTING DOCUMENTATION	20
6	SIG	NATURE	21

I. LIST OF ABBREVIATIONS AND KEY TERMS

List of Abbreviations

Abbreviations	Description of abbreviations
AE	Adverse Event
ALP	Alkaline Phosphatase
ALT	Alanine Transaminase
ASP5354	Astellas Development Code for Pudexacianinium Chloride
AST	Aspartate Transaminase
ATC	Anatomical Therapeutic Chemical classification system
CI	Confidence Intervals
CRF	Case Report Form
CSR	Clinical Study Report
ECG	Electrocardiogram
eCRF	Electronic Case Report Form
FAS	Full Analysis Set
ICF	Informed Consent Form
ICH	International Conference on Harmonization
ISN	International Study Number
MedDRA	Medical Dictionary for Regulatory Activities
LN	Lymph node
mg	Milligrams
mL	Milliliter
PD	Protocol Deviation
PK	Pharmacokinetic
PKAS	Pharmacokinetic Analysis Set
SAE	Serious Adverse Event
SAF	Safety Analysis Set
SAP	Statistical Analysis Plan
SAS	Statistical Analysis System
SBR	Signal Background Ratio
SLN	Sentinel Lymph Node
TEAE	Treatment Emergent Adverse Event
TLF	Tables, Listings and Figures
WHO	World Health Organization

Version History SAP Version History Summary

The changes from the prior approved SAP that impact analyses are listed with the rationale in the table below.

SAP Version	Approval Date	SAP Section(s)	Change	Rationale	
1.0	03-Dec-21		Not Applicable Original Version		
1.1	07-Feb-22	4.2.6 4.2.8	Sections 4.2.6 and 4.2.8 added.	Prior history imaging medication treatment and SoC Visualization Agent used during biopsy details added in the document.	
		4.4.1.2	Histopathologic confirmation information added at patient level	Histopathologic confirmation aspects added at patient level as secondary objective.	
		4.5.2	Additional details for metastatic spread defined in 4.5.2	Details for comparing LNs detected with metastatic spread at lymph node level added as exploratory objective.	
2.0	07-Mar-22	Mar-22 4.2.7 Additional d study drug d defined in se 4.2.7.		Details for drug dosing information for volume prepared and administered from syringe added.	
		4.7.1	TEAE of Interest: Hypersensitivity SMQ by NCI-CTC Grade added.	Hypersensitivity SMQ by NCI- CTC Grade details will be summarized as TEAE of Interest.	
2.1	09-Aug-22	1.2	Dose Arm/IP Name	Dose Arm/IP Name updated according to Protocol Amendment 2.	
		4.5.1	SBR added	SBR definition and imputation in case of 'Not Visualized' added.	
		4.6.1	Green Coloration of Urine or Skin	Green Discoloration was replaced by Green Coloration of urine or skin according to Protocol Amendment 2.	

ISN/Protocol 5354-CL-1201

1 INTRODUCTION

This Statistical Analysis Plan (SAP) contains technical and detailed elaboration of the principal features of the analysis described in the protocol, and includes procedures for executing the statistical analysis to fulfil the objectives of the study.

The final SAP will be approved before first subject screened.

If there are any changes from the planned analyses in the final version of the SAP that impact the statistical analyses, then it will be documented in the Clinical Study Report (CSR).

1.1 Objectives and Endpoints

1.1 Objectives and Endpoints	
Objectives	Endpoints
Primary	
 To determine the optimal dose of locally administered ASP5354 for 	 Optimal dose determination by the VRC based on:
LN visualization in participants	 LN tissue visualized (Yes/No)
undergoing SLN biopsy.	 Visualized tissue is lymphatic ir origin based on pathologic confirmation
	 The Likert Scale determination of the intensity of fluorescence (0 to 3)
	 Proportion of identified LN with histopathologic confirmation of LN tissue by ASP5354 compared with SoC treatment with either Tc-99mSC (approved drug) or Lymphoseek (generic name tilmanocept)
Secondary	
 To evaluate LN visualization of locally administered ASP5354 in participants undergoing SLN biopsy 	 Proportion of participants with at least 1 LN detected by visualization (Yes/No) with histopathologic confirmation of LN tissue using ASP5354
To compare LN detection for ASP5354 with the technetium-based treatment in breast cancer and melanoma	 Proportion of identified LN with histopathologic confirmation of LN tissue by ASP5354 compared with SoC treatment with either Tc- 99mSC or Lymphoseek

ISN/Protocol 5354-CL-1201

Objectives	Endpoints		
To investigate the safety and tolerability of locally administered	 Vital signs (blood pressure, pulse and respiratory rate) 		
ASP5354 in participants undergoing SLN biopsy	• Routine 12-lead ECGs		
SLIN biopsy	 Clinical laboratory tests (hematology [complete blood count], serum chemistry and urinalysis) 		
	Nature, frequency and severity of TEAEs and SAEs		
To investigate the pharmacokinetics of locally administered ASP5354 in participants undergoing SLN biopsy	• Plasma concentrations of ASP5354		
Exploratory			
To explore the visualization characteristics of ASP5354	 The Likert Scale for qualitative response about the intensity of fluorescence 		
	Signal background ratio		
	 Transdermal visualization of lymphatic spread of ASP5354 after injection (Yes/No) 		
	• Time from injection to surgical identification of LN(s)		
	 Number of LNs visualized by ASP5354 		
To compare LNs detected with metastatic spread for ASP5354 with the technetium-based treatment	 Proportion of LN with metastatic spread, based on histopathologic review, detected by ASP5354 compared with SoC treatment with either Tc-99mSC or Lymphoseek 		

Abbreviations from table above: ECG: electrocardiogram; LN: lymph node; SAE: serious adverse event; SLN: sentinel lymph node; SoC: standard of care; Tc-99mSC: Technetium-99m sulfur colloid; TEAE: treatment-emergent adverse event; VRC: Visualization Review Committee.

1.2 Study Design

The study is an open-label, dose-finding study to determine the optimal dose for LN visualization, as part of lymphatic mapping, in adult participants with breast cancer and melanoma undergoing SLN biopsy as part of cancer treatment.

Enrollment of breast cancer and melanoma participants will be performed independently and simultaneously. Dose level 2 (0.2 mg) will enroll the first 3 participants and then the VRC will review the data for the breast cancer group and the melanoma group separately. If LN visualization, with histopathologic confirmation, occurs in 3 participants, then 3 participants each will be enrolled first in 0.05 mg, and then in 0.6 mg dose levels. An interim analysis will then be performed across initial dose levels (0.05, 0.2 and 0.6 mg) in each cohort for breast cancer and melanoma by the VRC prior to further enrollment of participants. If < 3 participants at 0.2 mg have LN visualization with histopathologic confirmation on VRC review, then 3 participants will be enrolled sequentially in 0.6 mg and 1 mg. An interim analysis will then be performed across initial dose levels (0.2, 0.6 and 1 mg) in each cohort for breast cancer and melanoma by the VRC prior to further enrollment of participants.

Breast Cancer

Dose Arm/IP Name	ASP5354 Dose Level	ASP5354 Dose Conc and Volume	Number of Participants
Breast Cancer 0.05 mg/ ASP5354	0.05 mg	1.0 mg/mL, 0.05 mL in total	Up to 12
Breast Cancer 0.2 mg/ ASP5354	0.2 mg	1.0 mg/mL, 0.2 mL in total	Up to 12
Breast Cancer 0.6 mg/ ASP5354	0.6 mg	1.0 mg/mL, 0.6 mL in total	Up to 12
Breast Cancer 1 mg/ ASP5354	1 mg	1.0 mg/mL, 1 mL in total	Up to 12
Breast Cancer 2 mg/ ASP5354	2 mg	1.0 mg/mL, 2 mL in total	Up to 12
Breast Cancer 4 mg/ ASP5354	4 mg*	1.0 mg/mL, 4 mL in total	Up to 12

IP: investigational product

Melanoma

Dose Arm/IP Name	ASP5354 Dose Level	ASP5354 Dose Conc and Volume	Number of Participants
Melanoma 0.05 mg/ ASP5354	0.05 mg	1.0 mg/mL, 0.05 mL in total	Up to 12
Melanoma 0.2 mg/ ASP5354	0.2 mg	1.0 mg/mL, 0.2 mL in total	Up to 12
Melanoma 0.6 mg/ ASP5354	0.6 mg	1.0 mg/mL, 0.6 mL in total	Up to 12
Melanoma 1 mg/ ASP5354	1 mg	1.0 mg/mL, 1 mL in total	Up to 12
Melanoma 2 mg/ ASP5354	2 mg	1.0 mg/mL, 2 mL in total	Up to 12

IP: investigational product

Conc: concentration

^{*} The 4 mg dose level will be added only for breast cancer participants.

^{*} The 4 mg dose level will be added only for breast cancer participants

ISN/Protocol 5354-CL-1201

Depending on the outcome of the interim VRC data reviews, additional participants may be added to the same dose level, a dose may be closed, or a new dose (1 mg, 2 mg or 4 mg) will begin enrollment. Up to 12 participants will be assigned at each dose level for breast cancer and melanoma.

Details of the schedule of clinical assessments are available in the protocol (section 1.3).

1.3 Randomization

This is an open-label study. Participant enrollment and dispensation of IP will be performed via the interactive response technology (IRT) system. Prior to initiation of treatment, study site personnel will obtain the participant number and treatment assignment from the IRT system. Specific IRT procedures will be described in the respective study manual.

2 STATISTICAL HYPOTHESES

No statistical hypothesis is planned.

3 ANALYSIS SETS

In accordance with International Conference on Harmonization (ICH) recommendations in guidelines E3 and E9, the following analysis sets will be used for the analyses.

The determination of whether participants are included or excluded from the safety analysis sets will be made prior to database lock, except the pharmacokinetic analysis set.

Population	Description	
Enrolled	All participants who sign the ICF	
Full Analysis Set (FAS)	All participants who are enrolled and	
	receive study IP. Participants will be	
	analyzed according to the IP they actually	
	received.	
Safety Analysis Set (SAF)	All participants who are enrolled and	
	receive study IP. Participants will be	
	analyzed according to the IP they actually	
	received. SAF is the same as FAS for this	
	study.	
Pharmacokinetic analysis	All participants who receive at least 1 dose	
set (PKAS)	of IP for which at least 1 plasma	
	concentration data are available with the	
	time of dosing and sampling. Inclusion of	
	participants in the PKAS with missing data	
	or important protocol deviations will be	
	considered by the pharmacokineticist on a	
	case-by-case basis.	

ISN/Protocol 5354-CL-1201

4 STATISTICAL ANALYSES

A Statistical Analysis Plan (SAP) will be written to provide details of the analysis, along with specifications for tables, listings and figures to be produced. Changes from the planned analyses in the final SAP that impact the statistical analyses will be justified in the Clinical Study Report (CSR).

4.1 General Considerations

For continuous variables, descriptive statistics will include the number of subjects (n), mean, standard deviation, median, minimum and maximum. When needed, the use of other percentiles (e.g. 10%, 25%, 75% and 90%) will be mentioned in the relevant section.

Summaries based on FAS (e.g. efficacy data) will be presented by planned dose level, unless specifically stated otherwise. Safety analysis and other summaries based on SAF will be presented by actual dose level received.

The 95% confidence interval (95% CI) in proportion is based on exact method unless specifically stated otherwise.

Pharmacokinetic summaries based on PKAS will be presented by actual dose level received.

All data processing, summarization, and analyses will be performed using SAS® Version 9.3 or higher on Unix. Specifications for table, figure, and data listing formats can be found in the TLF specifications for this study.

Unless otherwise specified, all summaries will be presented by tumor type and dose level.

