7.1.1 Primary and Secondary Efficacy Assessments

Either during or post-operatively, the investigator will evaluate the details of all the LNs identified either by ASP5354 or Gamma Probe. These data will be captured to eCRF.

Following data is captured in eCRF per participant.

- Identification of at least 1 LN detected by ASP5354 and/or Tc-99mSC or Lymphoseek
- Times of injection of ASP5354 and Tc-99mSC or Lymphoseek
- Location (i.e., 3 and 9 o'clock) of ASP5354 administration
- Time of start of surgery
- Time of surgical identification of the LN(s) by ASP5354
- Time of incision for lymphatic mapping
- Time of removal of first LN
- Time of end of surgery
- Transdermal visualization of lymphatic spread of ASP5354 after injection

Following data is captured in eCRF per LN.

- “Sentinel LN” or “Non-sentinel LN”
- Method of identification (ASP5354 and/or Tc-99mSC or Lymphoseek)
- Dissection of LN tissue identified*
- Histopathologic confirmation of LN tissue by pathologist*

- Histopathologic confirmation of metastatic spread by pathologist*
- Likert scale:
The intensity of fluorescence will be qualitatively assessed during surgery by the investigator, by direct examination of the LN. Likert Scale (0 = None, 1 = Mild, 2 = Moderate and 3 = Strong) will be used to determine the intensity of fluorescence at the time point of the LN identification.
- Radioactivity count:
The radioactivity count of all the LNs identified by ASP5354 and /or Tc-99mSC or Lymphoseek will be counted with gamma probe.
* may not be collected in case of Non-Sentinel LN

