9.3.3 Secondary Endpoint(s)/Estimand(s) Analysis

The proportion of participants with at least 1 LN detected by visualization with histopathologic confirmation of LN tissue using ASP5354 will be estimated with exact 95% confidence interval (CI) by dose group.

The proportion of identified LNs with histopathologic confirmation of LN tissue will be estimated with exact 95% CI for ASP5354 by dose group and SoC treatment with either Tc-99mSC or Lymphoseek.

The secondary endpoint analysis will be performed using the FAS.

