4.4.1 Definition of Endpoints

4.4.1.1 Lymph Node Level

- The number of LN identified intraoperatively.
- The number and percentage ^{a)} of LN identified intraoperatively by histopathologic confirmation.
- The number of sentinel LN identified intraoperatively.
- The number and percentage ^{b)} of sentinel LN identified intraoperatively by histopathologic confirmation.
 - a) The denominator is the number of LN identified intraoperatively.
 - b) The denominator is the number of sentinel LN identified intraoperatively.

Sentinel LN detailed:

- The number of sentinel LN identified by ASP5354 or SoC treatment with either Tc-99mSC or Lymphoseek.
- The number of sentinel LN identified by ASP5354 and SoC treatment with either Tc-99mSC or Lymphoseek.
- The number and percentage ^{c)} of sentinel LN identified by ASP5354 or SoC treatment with either Tc-99mSC or Lymphoseek with histopathologic confirmation.
- The number of sentinel LN identified by ASP5354.
- The number and percentage ^{c)} of sentinel LN identified by ASP5354 with histopathologic confirmation and 95% CI.
- The number of sentinel LN identified by SoC treatment with either Tc-99mSC or Lymphoseek.
- The number and percentage ^{c)} of sentinel LN identified by SoC treatment with either Tc-99mSC or Lymphoseek with histopathologic confirmation and 95% CI.
- The difference in proportion of identified sentinel LN with histopathologic confirmation of LN tissue between ASP5354 and SoC treatment with either Tc-99mSC or Lymphoseek and 95% CI.
 - c) The denominator is the number of sentinel LN identified intraoperatively by histopathologic confirmation.

ISN/Protocol 5354-CL-1201

LN detailed:

- The number of LN identified by ASP5354 or SoC treatment with either Tc-99mSC or Lymphoseek.

- The number of LN identified by ASP5354 and SoC treatment with either Tc-99mSC or Lymphoseek.
- The number and percentage ^{d)} of LN identified by ASP5354 or SoC treatment with either Tc-99mSC or Lymphoseek with histopathologic confirmation.
- The number of LN identified by ASP5354.
- The number and percentage ^{d)} of LN identified by ASP5354 with histopathologic confirmation* and 95% CI.
- The number of LN identified by SoC treatment with either Tc-99mSC or Lymphoseek.
- The number and percentage ^{d)} of LN identified by SoC treatment with either Tc-99mSC or Lymphoseek with histopathologic confirmation* and 95% CI.

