- The difference in proportion of identified LN with histopathologic confirmation of LN tissue between ASP5354 and SoC treatment with either Tc-99mSC or Lymphoseek and 95% CI.
 - d) The denominator is the number of LN identified intraoperatively by histopathologic confirmation

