4.4.1.2 Patient Level

- The number of LN identified intraoperatively per patient.
- The number of LN identified by histopathologic confirmation per patient.
- The number of LN identified by ASP5354 with histopathologic confirmation per patient.
- The number of LN identified by SoC treatment with either Tc-99mSC or Lymphoseek with histopathologic confirmation per patient.
- The number of LN identified by ASP5354 or SoC treatment with either Tc-99mSC or Lymphoseek with histopathologic confirmation per patient.
- The number of LN identified by ASP5354 and SoC treatment with either Tc-99mSC or Lymphoseek with histopathologic confirmation per patient.
- Proportion of participants with at least 1 LN detected with histopathologic confirmation of LN tissue using ASP5354 and 95% CI.
- Proportion of participants with at least 1 LN detected with histopathologic confirmation of LN tissue using SoC treatment with either Tc-99mSC or Lymphoseek and 95% CI.

ISN/Protocol 5354-CL-1201

 The difference in proportion of identified LN with histopathologic confirmation of LN tissue between ASP5354 and SoC treatment with either Tc-99mSC or Lymphoseek and 95% CI.

 Proportion of participants with at least 1 LN with histopathologic confirmation detected by the method other than ASP5354 or SoC treatment with either Tc-99mSC or Lymphoseek and 95% CI.

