4.4.2 Main Analytical Approach

4.4.2.1 Lymph Node Level

The number of and percentage for lymph nodes or sentinel lymph nodes will be summarized per the specified denominator.

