4.5.2 Lymph Node Level

- The number and percentage ^{e)} of LN with metastatic spread, based on histopathologic review, detected by ASP5354

ISN/Protocol 5354-CL-1201

- The number and percentage ^{e)} of LN with metastatic spread, based on histopathologic review, detected by SoC treatment with either Tc-99mSC or Lymphoseek

- The difference in proportion of LN with metastatic spread, based on histopathologic confirmation of LN tissue between ASP5354 and SoC treatment with either Tc-99mSC or Lymphoseek and 95% CI
 - e) The denominator is the number of LN identified intraoperatively by histopathologic confirmation

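### Node-level exact 95% CIs treat nodes from one participant as independent, and no interval that is both paired and clustered is named for the ASP5354-minus-SoC difference (minor)

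*SAP*

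**What the plan says.** **Node-level proportions.** Protocol 9.3.3 states: "The proportion of identified LNs with histopathologic confirmation of LN tissue will be estimated with exact 95% CI for ASP5354 by dose group". It asks for the same for standard of care (SoC). SAP 4.1 makes exact intervals the default: "The 95% confidence interval (95% CI) in proportion is based on exact method unless specifically stated otherwise". SAP 4.4.1.1 requests 95% CIs for the ASP5354 and SoC percentages, for sentinel nodes and for all nodes. The only method text for this level, SAP 4.4.2.1, reads: "The number of and percentage for lymph nodes or sentinel lymph nodes will be summarized per the specified denominator".

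**Node-level difference.** SAP 4.4.1.1 also asks for a 95% CI for "The difference in proportion of identified sentinel LN with histopathologic confirmation of LN tissue between ASP5354 and SoC treatment", and for the same quantity over all nodes. Both agents share one denominator; for all nodes, "The denominator is the number of LN identified intraoperatively by histopathologic confirmation". Protocol 4.1 gives every participant both agents, and protocol 7.1.1 records for each node "Method of identification (ASP5354 and/or Tc-99mSC or Lymphoseek".

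**Other places.** SAP 4.5.2 requests a 95% CI for "The difference in proportion of LN with metastatic spread, based on histopathologic confirmation of LN tissue between ASP5354 and SoC treatment". SAP 4.4.1.2, headed as patient level, lists proportions of participants for each agent and then "The difference in proportion of identified LN with histopathologic confirmation of LN tissue between ASP5354 and SoC treatment", which is worded as a proportion of nodes.

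No section names an allowance for clustering or pairing.

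**The concern.** Nodes from one participant share an injection, a drainage pattern and a surgeon, so their outcomes are likely to be correlated. A binomial interval on pooled nodes then credits the data with more information than they hold.

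The between-agent difference has a second feature. Both agents are scored on the same nodes, so the two percentages are not independent samples. The SAP states neither feature. Even if its default for a CI in a proportion is stretched to cover a difference, two programmers could produce different intervals from the same data.

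At stake is the stated precision of a secondary endpoint, the node-level comparison with SoC.

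**Working it through.** **The plan's own figures.** Up to 12 participants at each of 3 initial dose levels gives 3 × 12 = 36 per tumor type, as stated. There is no power calculation to reproduce. The nominal level also checks out under independence: 12 participants with exactly 3 nodes at rate 0.9 give exact-interval coverage of 95.4%.

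**Inputs.** From the documents: exact 95% intervals, and reviews in steps of 3 up to 12 participants per dose (SAP 4.9). The only detection rate given is above 90% for radioisotope or blue dye in breast cancer (protocol 2.2), with no unit stated. Assumed: 1–4 nodes per participant, ICC up to 0.5, rates mainly 0.8–0.95.

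**Single proportions.** For a participant with m nodes, the number detected is beta-binomial with parameters p(1−ICC)/ICC and (1−p)(1−ICC)/ICC. The node total n and detected total x are convolved over participants. The exact limits are the 0.025 quantile of Beta(x, n−x+1) and the 0.975 quantile of Beta(x+1, n−x). Coverage is the summed probability of outcomes whose limits contain p.

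| Participants | Nodes each | Rate | ICC 0.3 | ICC 0.5 |
|---|---|---|---|---|
| 12 | 1–2 | 0.8–0.95 | at least 95% | at least 94% |
| 12 | 1–4, equally likely | 0.8 | 92% | 88% |
| 12 | 1–4, equally likely | 0.9 | 95% | 93% |
| 12 | exactly 3 | 0.9 | 88% | 82% |
| 12 | exactly 3 | 0.95 | 97% | 95% |
| 6 | 1–4, equally likely | 0.8 | 94% | 91% |
| 3 | exactly 4 | 0.8 or 0.95 | 93% | about 90% |

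At ICC 0.2, the second row gives 94%. The 1–2 node result depends on the rate range: with exactly 2 nodes, 12 participants and rates from 0.60 to 0.97, mean coverage is 95.2% at ICC 0.3 and 93.5% at ICC 0.5, with minima of 91.7% and 89.2%.

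The design effect 1 + (m−1) × ICC shows why. With 12 × 3 = 36 nodes, it is 1.6 at ICC 0.3 and 2.0 at ICC 0.5, so the data carry the information of 36/1.6 = 22.5 or 36/2 = 18 independent nodes. The exact method's built-in conservatism absorbs part of this loss, and more of it when nodes are few or the rate is near 1.

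**Difference.** Let a and b be the ASP5354 and SoC rates over the common denominator, and u the share of those nodes missed by both. Then P(both detect) = a + b − 1 + u, and the within-node covariance is u − (1−a)(1−b). A node missed by both agents enters the denominator only if another method found it. SAP 4.4.1.2 allows for such nodes, but u is likely to be small. With u = 0, the covariance is −(1−a)(1−b), which is never positive.

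Example: a = 0.80, b = 0.90, u = 0.
- Covariance: −0.20 × 0.10 = −0.02.
- Per-node variance of the difference: 0.16 + 0.09 + 2 × 0.02 = 0.29.
- Unpaired variance: 0.16 + 0.09 = 0.25.
- Standard-error ratio: √(0.29/0.25) = 1.08.

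Ignoring pairing therefore makes the interval about 7% too narrow (1 − 1/1.08) in this example, before any clustering. Clustering can narrow it further. In a latent-normal simulation at 12 × 3 nodes and 0.80 against 0.90, with strong clustering and no between-agent correlation, an unpaired Newcombe interval covered 87.7%. With independent nodes and a positive correlation of 0.5 it covered 98.0%, but that simulation does not restrict nodes missed by both agents as the SAP denominator does. Newcombe is a stand-in here; the SAP does not name it.

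**The case against.** The strongest reply is that these intervals are descriptive. SAP 2 plans no hypothesis, and SAP 4.3 and 4.4 exclude testing. Under SAP 4.3.1 and 4.3.2 the Visualization Review Committee uses the proportion itself, the totality of data and individual listings. Participant-level exact CIs, with the right unit, are already planned for both agents. All of this stands, and it makes the point minor. A reader might infer that the dose selection is compromised. The documents do not support that, because no selection rule refers to an interval.

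A second reply is that the size depends on undocumented inputs. That also stands. A reader might infer that under-coverage is established; it is only possible, and it disappears in several plausible settings. Nor do the results for varying node counts bound the effect: at 12 participants, rate 0.9 and ICC 0.5, coverage is 93% with 1–4 nodes each but 82% with exactly 3. The opposite inference, that cohorts of 3 are safe, fails as well.

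Third, clustered intervals have their own small-sample problems. This stands too, and it limits what the fix can promise.

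Finally, the TLF specifications cited in SAP 4.1 were not available. The SAP cites them for output formats, so a method could appear there, but the SAP does not say so.

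**Conclusion.** The point holds as a minor one. The stated method assumes independent nodes. Coverage can fall below 95% at any cohort size once participants contribute about 3–4 correlated nodes, to between about 82% and 94% in the unfavourable settings tabulated. It stays near or above 95% with 1–2 nodes each at rates of 0.8–0.95. These figures rest on assumed node counts, ICC and rates.

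The difference is paired within node and clustered by participant, and the SAP names no interval that reflects either feature. A reader might assume the usual positive pairing correlation and conclude that an unpaired interval is safely wide. The common denominator argues against that: the within-node correlation will tend to be negative and an unpaired interval too narrow, unless other methods find many nodes that both agents missed.

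The effect is confined to the descriptive precision of a secondary endpoint and of the exploratory metastatic-node difference. The unit mismatch in SAP 4.4.1.2 is a wording defect that needs no calculation.

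**What to change.** 1. **SAP 4.4.1.1, proportions.** Replace the plain exact CI with a participant-clustered interval. One example is Clopper-Pearson on a Korn-Graubard effective sample size with the degrees-of-freedom adjustment, capped at the node count. Fall back to the plain exact CI when the between-participant variance is zero or there are only about 3 participants. Say that this improves coverage without guaranteeing 95% in small cohorts: it reached about 89–90% at 12 × 3 nodes (rate 0.9, ICC 0.5) and 90–91% at 6 × 3 (rate 0.8, ICC 0.5). Footnote every plain exact node-level CI, including fallbacks, as assuming independent nodes and possibly too narrow.
2. **SAP 4.4.1.1, differences.** State that the comparison is paired within node and clustered by participant. Name an interval that reflects both, and label it approximate. A participant-clustered paired t interval is one candidate: at 0.80 against 0.90 with strong clustering it covered 92.6–94.4% for 12 × 3 nodes, and it covered about 88–94% in settings with 6 participants.
3. **SAP 4.5.2.** Report the metastatic-node difference descriptively, or label its CI as assuming independence. Eligible participants are N0, so some cohorts may have no metastatic node at all.
4. **SAP 4.4.1.2.** Reconcile the patient-level difference with the participant proportions listed before it. If a participant-level difference is meant, use a paired-proportion CI such as the Tango score interval.

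**Cost.** SAP wording and a little programming, with no new data. Intervals become somewhat wider: in runs with varying node counts and ICC 0–0.5, a Korn-Graubard interval averaged 5–48% wider at 12 participants and 7–47% at 6. Those figures are indicative only, since they do not cover fixed node counts.
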